6.4.1.7. Overall Response Assessment

The overall response assessment takes into account response in both target and non-target lesions, the appearance of new lesions, current corticosteroid use (compared to screening/baseline) and neurologic symptoms/examination (clinical status) according to the criteria described in [Appendix C](#).

Subjects who do not meet the criteria for an objective response or disease progression by the end of Cycle 6 (end of Cycle 3 for DIPG subjects) will be considered as having long-term SD.

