9.3. Sample Size and Power Considerations

Under Simon's Optimal two-stage design with a 5% significance level and 90% power, assuming a lower boundary of interest in the response rate of 10% and an upper boundary of interest in the

response rate of 40%, a total of 20 subjects evaluable for the primary endpoint (ie, Response Population) are required per stratum; 9 per stratum in Stage 1 and an additional 11 per stratum in Stage 2.

Enrollment will proceed as follows:

1. Stage 1: Nine subjects will be enrolled into each of the strata.
2. Stage 2: If during Stage 1, ≥ 2 subjects in a given stratum achieve either an OR (either CR or PR) within the first 6 cycles of treatment (within 3 cycles for DIPG) or a long-term SD, an additional 11 subjects shall be enrolled to that stratum; otherwise no additional subjects will be enrolled.
3. If a total of 5 or more subjects across all 20 subjects in a given stratum (Stage 1 and 2) evaluable for the primary endpoint are observed as having either an OR (either CR or PR) within the first 6 cycles of treatment (within 3 cycles for DIPG) or long-term SD, pomalidomide will be considered effective in that disease indication.

Up to 80 subjects (36 subjects in Stage 1 and 44 subjects in Stage 2) will be included should all strata enroll the maximum number of subjects (ie, 20 per stratum), assuming no subjects are replaced.

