9.8. Interim Analysis

For each stratum, there is one interim analysis planned at the end of Stage 1. The interim analysis will be informal, performed internally by Celgene personnel with input, only if needed, from the DMC and steering committee (SC). Enrollment will be suspended for each interim analysis, once the first 9 subjects evaluable for the primary endpoint have been enrolled. Enrollment for each stratum will be re-opened/closed based upon the following criteria:

- Should only one or no subjects be observed as having either an OR (either CR or PR) or a long-term SD, that stratum shall be closed to further enrollment.
- Should at least 2 subjects across Stage 1 have either an OR (either CR or PR) or a long-term SD, then that stratum will continue into Stage 2 to include up to 11 more additional subjects evaluable for the primary endpoint.

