Appendix C: Overall Response Assessment

The overall response assessment takes into account response in both target (Appendix B) and non-target lesions (Appendix B), the appearance of new lesions, current corticosteroid use (compared to baseline) and neurologic symptoms/examination (clinical status) according to the criteria below (Table 10). Subjects who do not meet the criteria for an objective response or disease progression by the end of Cycle 6 (end of Cycle 3 for DIPG subjects) will be considered as having long-term SD.

Table 10: Overall Response Assessment

Criterion	Overall Response				
	Complete Response	Partial Response		Stable Disease	Progression
Target lesions	CR	PR	CR	SD	PD
Non-Target lesions	CR	CR or IR/SD	IR/SD	CR or IR/SD	PD
New Lesion	None	None	None	None	Present
Corticosteroids	None ^a	Stable or Decreasing ^b	Stable or Decreasing ^b	Stable or Decreasing ^b	Not Applicable ^c
Clinical Status (neurologic examination)	Stable or Improved	Stable or Improved	Stable or Improved	Stable or Improved	Decreasing ^d
Requirement for Response	All	All	All	All	Any ^e

CR = complete response; IR = incomplete response; PR = partial response; SD = stable disease; PD = progressive disease.

^a Only physiologic replacement doses allowed, defined as no more than 0.75 mg/m²/day of dexamethasone or equivalent.

^b Not greater dose than compared with baseline.

^c An increase in corticosteroid dose alone will not cause a determination of progression in the absence of clinical deterioration or radiographically documented lesion growth.

^d Neurologic abnormalities or worsening neurologic status not explained by causes unrelated to tumor progression (eg, anticonvulsant or corticosteroid toxicity, wean, electrolyte disturbances, sepsis, hyperglycemia, etc.) or changes in corticosteroid dose.

^e Progression occurs when any of these criteria are met present.

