4.4. Overall Study Design and Plan

[figure not shown]
Each tumor type/disease indication incorporates the Simon's Optimal Two-stage study design incorporating the following parameters: significance level of 5%, 90% power and a lower and upper boundary of interest of 10% and 40%, respectively, of the primary endpoint. Based on these boundaries, each tumor type/disease indication will enroll up to 20 subjects eligible for the primary endpoint; 9 in stage one and 11 in stage two. Subjects not eligible for the primary endpoint, ie, not contained within the Response Population, If the number of subjects observed with either an OR or long-term SD according to central response review is ≥ 2 , then enrollment shall continue into stage two; otherwise enrollment will close to that specific tumor type/disease

indication. At the end of stage two, if ≥ 5 out of 20, ie, the target ORSDR $\geq 25\%$, of the subjects enrolled across stage one and stage two combined are observed as having an OR or long-term SD then the treatment will be declared positive in that given tumor type/disease indication; otherwise the treatment will be considered negative in that given tumor type/disease indication (

Figure 2).

If, in a given tumor type/disease indication, by the time the eighteenth subject becomes evaluable for the primary endpoint and only two subjects have been observed across stage 1 and stage 2 combined as having either a OR or long-term SD then enrollment to that tumor type/disease indication will be stopped due to a lack of efficacy.

Figure 1: Overall Study Design

[figure not shown]

ICF=informed consent form, IAF=informed assent form, MRI=magnetic resonance imaging, OS=overall survival, PD=disease progression, PFS=progression-free survival, SAE=serious adverse event, SPM=second primary malignancy.

*From last subject enrolled

**Subjects without a PD at time of treatment discontinuation will continue to be followed for MRI tumor assessment (every 6 months for the first year from treatment discontinuation, then annually thereafter).

Figure 2: Simon’s Optimal Two-stage Parallel Phase 2 Study Design

DIPG=diffuse intrinsic pontine glioma, OR=objective response, PD=progressive disease, LTSD= Long-term stable disease.

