6.1. Analysis of Primary Efficacy Endpoint

6.1.1. Objective Response and Long-term Stable Disease Rate

The ORSDR is defined as the percentage of subjects that achieve either a CR, PR or SD maintained for ≥ 6 cycles (≥ 3 cycles for the DIPG tumor type/disease indication) as their best response, divided by the total number of subjects available for the analysis within the given population, eg, subjects contained within the Response Population (primary analysis), the ITT Population, and the Safety Population as outlined within Section 5 of this SAP. The ITT Population will not be used should all enrolled subjects have received at least one dose of study drug. Non-responder subjects are considered subjects with a PD as best response, subjects not having a postbaseline assessment or subjects having not evaluable recorded on their postbaseline assessment(s). The corresponding 2-sided, 95% Clopper-Pearson confidence interval (CI) will also be provided.

Calculation of SD duration starts at the time of first dose of pomalidomide and continues until the date of the first observation of PD is recorded or death due to any cause, regardless of whether the subject achieves a CR and/or PR within that period, or until the date of the last disease assessment if no PD or death is recorded; if the difference is ≥ 6 cycles (≥ 3 cycles for the DIPG tumor type/disease indication), ie, the subject has not had a documented PD before Cycle 7, Day 1 (Cycle 4, Day 1 for the DIPG tumor type/disease indication) and has completed 6 cycles of pomalidomide (3 cycles for the DIPG tumor type/disease indication), then the SD will be considered as being maintained for ≥ 6 cycles (≥ 3 cycles for the DIPG tumor type/disease indication).

For identification of PD for this SD duration calculation, PD is classified as a PD as observed during a response assessment (both during the Treatment Period and the Follow-up Period if applicable); the first time this occurrence is observed is selected as the PD date.

Disease assessments recorded on or after start of a new anticancer therapy will not be considered, nor will disease assessments reported after a PD has been observed.

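### The protocol's default sentence awards long-term stable disease to subjects who fail Table 10's stable-disease criteria on steroid dose; the SAP narrows this gap but does not close it

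*Protocol*

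**What the plan says.** **Table 10 (Protocol Appendix C).** Overall SD requires all listed criteria: target and non-target lesions, no new lesion, corticosteroids, and clinical status. The steroid criterion is explained in footnote b: "Not greater dose than compared with baseline". Footnote c adds: "An increase in corticosteroid dose alone will not cause a determination of progression", unless there is clinical deterioration or lesion growth. Section 6.4.1.6 repeats this.

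**Default sentence (Protocol Summary, Section 6.4.1.7, Appendix C).** A subject with neither objective response (OR) nor PD when Cycle 6 ends (Cycle 3 for DIPG) "will be considered as having long-term SD". The sentence does not require the SD criteria to be met or the cycles to be completed.

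**Endpoint definition (Protocol 9.6).** Long-term SD is SD held for at least 6 cycles (3 for DIPG). It counts as a success in the primary endpoint, ORSDR.

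**SAP 6.1.1.** The best response must be CR, PR or SD of sufficient duration. Subjects with PD as best response, with no post-baseline assessment, or recorded as not evaluable are non-responders. SD counts as maintained if "the subject has not had a documented PD before Cycle 7, Day 1" (Cycle 4 Day 1 for DIPG) and 6 (3) cycles of drug were completed. SAP 6.2.2 uses the same duration rule. Neither section mentions steroids.

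**Decisions.** A stratum closes after Stage 1 under this condition: "Should only one or no subjects be observed as having either an OR (either CR or PR) or a long-term SD". It is declared effective with 5 or more successes among 20 (Protocol 9.3).

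**The concern.** Appendix C contains both a set of SD criteria and a sentence that bypasses them. The subject affected is a child whose scan and neurologic status are stable but whose steroid dose is above baseline. Table 10 withholds SD from that child, while the default sentence records a success.

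Misclassification here runs one way. It can turn a non-success into a success and never the reverse. It acts on the single composite that decides both whether a stratum opens Stage 2 and whether the drug is called effective, and both thresholds are small counts.

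There is a second inconsistency. Because the default sentence has no completed-cycles condition, the protocol and SAP classify differently a child who stops early without PD after at least one post-baseline scan.

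**Working it through.** **1. Who falls between the categories.** Take a child with target lesions SD, non-target lesions IR/SD, no new lesion, stable clinical status, and a steroid dose above baseline.

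- CR or PR: no, because the lesion criteria are not met.
- SD: no, because all criteria are required and the steroid criterion fails.
- PD: no, because a steroid rise alone does not qualify.

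A scan with at least 50% shrinkage on a raised dose also fits no column, because PR carries the same steroid criterion.

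**2. How each rule classifies the subject.**

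| Subject | Protocol default sentence | SAP 6.1.1 |
|---|---|---|
| SD reading first, raised dose at later assessments, no PD, 6 (3) cycles completed | success | success |
| Raised dose at every assessment, no PD, cycles completed | success | depends on coding; non-responder if recorded as not evaluable |
| Stops after Cycle 1 but before Cycle 6 (3), no PD, has a post-baseline scan | success, read literally | not long-term SD |
| Completed at least one cycle, no post-baseline assessment | non-responder (Protocol 9.2) | non-responder |

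The second row matters most in DIPG, where the first scheduled post-baseline MRI is Cycle 4 Day 1 (Protocol 6.4.1). There is then only one scheduled scan from which to set the endpoint.

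**3. The plan's own design.** The inputs are a "significance level of 5%, 90% power and a lower and upper boundary of interest of 10% and 40%, respectively, of the primary endpoint" (SAP 4.4) and "9 per stratum in Stage 1 and an additional 11 per stratum in Stage 2" (Protocol 9.3). Stage 2 opens with 2 or more of 9, and 5 or more of 20 declares effectiveness. With success probability p,

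P(effective) = Σ over x = 2,…,9 of P[Bin(9,p) = x] × P[Bin(11,p) ≥ 5 − x].

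At p = 0.10:

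- x = 2: 0.17219 × 0.08956 = 0.01542
- x = 3: 0.04464 × 0.30264 = 0.01351
- x = 4: 0.00744 × 0.68619 = 0.00511
- x ≥ 5: 0.00089 × 1 = 0.00089
- Sum: 0.0349

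At p = 0.40 the same formula gives 0.902. The chance of stopping after Stage 1 at p = 0.10 is 0.775, so expected N is 9 + 11 × 0.225 = 11.48. An exhaustive search up to n = 32 returns this design as the optimal one, so the stated design reproduces.

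**4. Effect of default credit.** Let m be the fraction of true failures credited as long-term SD. The documents do not give m, so it is an assumption. For a stratum with a true rate of 10%, the observed rate is p = 0.10 + 0.90m.

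| m | p | P(Stage 2 opens) | P(declared effective) |
|---|---|---|---|
| 0 | 0.100 | 22.5% | 3.5% |
| 1% | 0.109 | 25.6% | 4.8% |
| 2.5% | 0.1225 | 30.4% | 7.3% |
| 5% | 0.145 | 38.3% | 12.7% |
| 10% | 0.190 | 53.3% | 27.7% |

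The stated 5% level is crossed between m = 1% and m = 2.5%.

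**The case against.** The case against giving this much weight has five parts.

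- **The SAP is stricter than the default sentence.** A reader might infer that both documents credit every child on a raised dose. They do not. SAP 6.1.1 first requires SD as best response and makes not-evaluable subjects non-responders. The SAP clearly miscredits only a child with at least one SD reading followed by raised-steroid assessments, because its duration rule does not re-test SD. This stands.
- **Early leavers.** A reader might also infer that subjects who leave early without PD inflate the primary analysis. The completed-cycles condition in SAP 6.1.1 removes them. What remains is a conflict between the documents' wording, not a bias in the SAP analysis. This stands.
- **Frequency.** Protocol 8.1.2 foresees steroid increases, but for worsening neurologic symptoms, which Table 10 may already class as PD. The gap needs a raised dose with stable clinical status and no PD through the landmark. The documents do not show how common that is. This stands.
- **Magnitude.** A failure with documented PD cannot be miscredited, so m is limited by the failures that remain PD-free. At m = 10%, false successes would be 0.90 × 10% = 9% of subjects, almost as many as the 10% true successes. The protocol also does not say under which definition of long-term SD the 10% boundary was set. The table therefore shows sensitivity and is not an estimate.
- **The independent review charter** (Protocol 6.4.1.8) may settle the coding. It is not among the documents, and a primary-endpoint rule should be readable from the protocol and SAP.

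These points narrow the affected group. They do not remove the contradiction inside Appendix C.

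**Conclusion.** The point holds in bounded form. The default sentence contradicts Table 10's all-criteria requirement for SD and the maintained-SD definition in Protocol 9.6. It makes a primary-endpoint success of a clinically stable child on a raised steroid dose who is not SD under the plan's own table. The SAP leaves a narrower gap, confined with certainty to an SD reading followed by raised-steroid assessments. The two documents also classify early leavers without PD differently, although the SAP analysis does not credit them.

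The direction is certain: the error can only add successes to the 2/9 and 5/20 decisions. The size is not known. If m is 1% to 10%, the chance of declaring a 10% stratum effective is 4.8% to 27.7%, against 3.5% by design. This assumes that the 10% boundary refers to SD as Table 10 defines it. A reader might infer from these figures that the trial's type I error is in fact inflated to some stated level. The documents give no rate of steroid increase among clinically stable subjects, so they do not support that.

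**What to change.** 1. Delete the default sentence from the Protocol Summary, Section 6.4.1.7 and Appendix C.
2. Use one definition of long-term SD in the protocol and in SAP 6.1.1 and 6.2.2: overall SD under all Table 10 criteria at the landmark central assessment (end of Cycle 6; end of Cycle 3 for DIPG), with 6 (3) cycles completed and no earlier PD.
3. For endpoint coding, state that an assessment that fits no Table 10 column because of steroid dose, whether the scan is stable or shrinking, is not SD, not OR and not PD. It then does not count as a success at that assessment.
4. Reconcile footnote b with the reference to physiologic replacement doses in Section 6.4.1.6, so that it is clear how such doses enter the overall response.

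The cost is wording in two documents. Steroid use and scans already enter the overall response, so no new assessment is needed, and the 9 + 11 design is unchanged. The change affects endpoint classification only, not treatment. The downside is that the observed rate may be slightly lower.

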Appendix D: Performance Status

Table 11: Performance Status

Karnofsky Scale (age ≥ 16 years)		Lansky Scale (age < 16 years)	
Able to carry on normal activity and to work; no special care needed.		Able to carry on normal activity; no special care is needed	
100	Normal no complaints; no evidence of disease	100	Fully active
90	Able to carry on normal activity; minor signs or symptoms of disease	90	Minor restriction in physically strenuous play
80	Normal activity with effort; some signs or symptoms of disease	80	Restricted in strenuous play, tires more easily, otherwise active
Unable to work; able to live at home and care for most personal needs; varying amount of assistance needed.		Mild to moderate restriction	
70	Cares for self; unable to carry on normal activity or to do active work	70	Both greater restrictions of, and less time spent in active play
60	Requires occasional assistance, but is able to care for most of his personal needs	60	Ambulatory up to 50% of the time, limited active play with assistance/supervision
50	Requires considerable assistance and frequent medical care	50	Considerable assistance required for any active play, fully able to engage in quiet play
Unable to care for self; requires equivalent of institutional or hospital care; disease may be progressing rapidly.		Moderate to severe restriction	
40	Disabled; requires special care and assistance	40	Able to initiate quiet activities
30	Severely disabled; hospital admission is indicated although death not imminent	30	Needs considerable assistance for quiet activity
20	Very sick; hospital admission necessary; active supportive treatment necessary	20	Limited to very passive activity initiated by others (eg, television)
10	Moribund; fatal processes progressing rapidly	10	Completely disabled, not even passive play
0	Dead	0	Unresponsive

Source: Karnofsky, 1949; Lansky 1987.

Appendix E: Plasma PK Sample Handling Instruction

Each participating institution will be provided with PK sample collection kits along with a PK laboratory manual.

Preparation of Collection Tubes and Storage Vials

All labels will be provided by central laboratory. The labels will contain the following information:

- Protocol No.: **CC-4047-BRN-001**
- Subject ID number: (To be added by site)
- Nominal Time (eg, 2 hours postdose)
- Sample Type (eg, Plasma Primary or Backup)

All plasma collection tubes and storage vials should be labeled and chilled on wet ice **prior to** sample collection and processing.

Pomalidomide Plasma PK Sample Handling

1. Blood Sample Collection

- Fill an ice bucket with a sufficient amount of ice to **pre-chill** all collection tubes before blood draw.
- Collect approximately 1 mL of whole blood into a pre-chilled **K2 EDTA** tube.
- Accurately record the time of blood collection.
- Gently invert the tube 3 to 5 times and immerse it into ice bath immediately to prevent possible compound degradation at room temperature.

2. Blood Sample Processing to Obtain Plasma

- **Within 30 minutes of collection**, the blood sample must be centrifuged at 1,500 g (about 3,000 rpm) for 10 minutes at 4°C to obtain plasma.
- Transfer approximately 0.25 mL of plasma into each of two pre-labeled, pre-chilled, polypropylene citric acid storage tubes (ie, primary and back up).
- Keep storage tubes on ice before they are ready to be transferred into a freezer.
- **Within 60 minutes of blood collection**, transfer plasma samples in storage vials into a -20°C freezer, where the tubes will remain stored until shipping.
- Immediately record the time of sample entry into the freezer.

PK Plasma Sample Shipment

All PK sample label information on the storage tubes have to be checked against the requisition form and then the samples must be shipped on dry ice from the sites to the central lab.

A copy of the completed specimen manifest must accompany the shipment, and must list the following information at minimum:

- Sponsor name: Celgene Corp
- Celgene Study Number: **CC-4047-BRN-001**
- Subject ID Numbers
- Collection date (eg, dd mmm yyyy)
- Nominal collection time (ie, 2 hours postdose)
- Sample types (eg, Plasma Primary or Backup)

The central lab will then ship the samples to XBL for sample analysis of pomalidomide.

Appendix F: Pomalidomide Dosing

Table 12: Pomalidomide Capsule Dosing Tables

2.6 mg/m²/day (Starting Dose)		
Minimum BSA (m²)	Maximum BSA (m²)	Daily Pomalidomide Dose (mg)
0.55	0.66	1.5
0.67	0.86	2.0
0.87	1.05	2.5
1.06	1.25	3.0
1.26	1.44	3.5
1.45	1.63	4.0
1.64	1.82	4.5
1.83	2.01	5.0
2.02	2.21	5.5
2.22	2.40	6.0
2.41	2.50	6.5
1.9 mg/m²/day (Dose Level -1)		
Minimum BSA (m²)	Maximum BSA (m²)	Daily Pomalidomide Dose (mg)
0.55	0.66	1.0
0.67	0.92	1.5
0.93	1.18	2.0
1.19	1.44	2.5
1.45	1.71	3.0
1.72	1.97	3.5
1.98	2.23	4.0
2.24	2.49	4.5
2.50	2.50	5.0

Table 12: Pomalidomide Capsule Dosing Tables (Continued)

1.3 mg/m²/day (Dose Level -2)		
Minimum BSA (m²)	Maximum BSA (m²)	Daily Pomalidomide Dose (mg)
0.55	0.66	0.5
0.67	0.96	1.0
0.97	1.34	1.5
1.35	1.73	2.0
1.74	2.11	2.5
2.12	2.50	3.0

BSA = body surface area.

Table 13: Pomalidomide Dosing Table – Oral Suspension

For subjects receiving pomalidomide as an oral suspension, please refer to the Pomalyst Oral Suspension Preparation Administration and Handling Guide for additional guidance.

Calculated Dose (mg/day)	Actual Dose Administered (mg/day)	Volume Administered (mL)
0.50 to 0.69	0.6	0.3
0.70 to 0.89	0.8	0.4
0.90 to 1.09	1.0	0.5
1.10 to 1.29	1.2	0.6
1.30 to 1.49	1.4	0.7
1.50 to 1.69	1.6	0.8
1.70 to 1.89	1.8	0.9
1.90 to 2.09	2.0	1.0
2.10 to 2.29	2.2	1.1
2.30 to 2.49	2.4	1.2
2.50 to 2.69	2.6	1.3
2.70 to 2.89	2.8	1.4
2.90 to 3.09	3.0	1.5
3.10 to 3.29	3.2	1.6
3.30 to 3.49	3.4	1.7
3.50 to 3.69	3.6	1.8
3.70 to 3.89	3.8	1.9
3.90 to 4.09	4.0	2.0
4.10 to 4.29	4.2	2.1
4.30 to 4.49	4.4	2.2
4.50 to 4.69	4.6	2.3
4.70 to 4.89	4.8	2.4
4.90 to 5.09	5.0	2.5
5.10 to 5.29	5.2	2.6
5.30 to 5.49	5.4	2.7
5.50 to 5.69	5.6	2.8
5.70 to 5.89	5.8	2.9

Table 13: Pomalidomide Dosing Table – Oral Suspension (Continued)

Calculated Dose (mg/day)	Actual Dose Administered (mg/day)	Volume Administered (mL)
5.90 to 6.09	6.0	3.0
6.10 to 6.29	6.2	3.1 ^a
6.30 to 6.49	6.4	3.2 ^a
6.50-6.69	6.6	3.3 ^a

^a For administered volumes > 3.0 mL, the dose should be split. For example, a volume of 3.2 mL can be administered as two doses of 1.6 mL each. A dose of 3.3 can be administered as two doses of 1.6 mL and 1.7 mL each.

Celgene Signing Page

This is a representation of an electronic record that was signed electronically in Livelink.
This page is the manifestation of the electronic signature(s) used in compliance with
the organizations electronic signature policies and procedures.

UserName: PPD

Title: PPD

